Study Type	 Cross-sectional observational screening study followed by an interventional clinical trial & observational follow- up study. Clinical Trial design: Prospective Randomised Open Blinded Endpoint (PROBE) design Phase III/IV Randomisation: Computer generated simple randomisation with allocation of study number and indicate treatment or no treatment
Date of First Enrolment	Anticipated June/July 2013.
Target Sample Size	500 participants recruited into the screening study with 130 then going on to be randomised into the clinical trial and 65 entering the observational follow-up study
Primary Outcome(s)	Study primary outcome: Change in Left Ventricular Mass Index on cardiac Magnetic Resonance Imaging (cMRI) in the randomised clinical trial comparing active treatment with usual care. Metric/method of measurement – grams per metre squared Timepoint – Baseline and Study end (12 months following treatment initiation).
Key Secondary Outcomes	 Secondary outcomes: The following outcome measures will be assessed at baseline and study end (12 months following treatment initiation): 1. Change in Left Ventricular Mass to volume ratio on cMRI Metric/method of measurement – grams per millilitre cubed 2. Regional systolic & diastolic strain Metric/method of measurement – % change in dimension by cMRI myocardial tissue tagging 3. Interstitial Fibrosis using T1 mapping Metric/method of measurement – Fibrosis index by cMRI 4. Aortic distensibility on cMRI Metric/method of measurement (10⁻³/kPa) 5. Aortic & Carotid wall thickness on cMRI Metric (micometers)

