6.3.1.8 Defining the LOW CASP and HIGH CASP Groups - Stratification According CASP

After 500 participants have been recruited into the stage 1 screening study, data from participants will be stratified according to their CASP values. Based on the distribution of CASP values from our previous studies, we will select the upper 25% of CASP values to define the HIGH CASP group (n=130) who will be invited to participate in the RCT if the study progresses to the second stage. We will also select 65 participants with the lowest CASP values who will form the LOW CASP observational cohort and will be invited to participate in the observational follow-up study. Our preliminary data suggests that stratifying the stage 1 study population in this manner will result in an upper limit CASP value for the LOW CASP group of 129mmHg, and lower limit value for the HIGH CASP groups. We recognise that this will most likely generate two groups with different brachial BP values as well different CASP values. However, according to current guidance, treatment would not be offered on the basis of the brachial BP value alone. Furthermore, CASP cannot be predicted from the brachial BP and we are specifically evaluating the use of CASP to stratify the patients for treatment.

We plan to screen up to 500 participants in Stage 1 of the study, however, as screening proceeds, the distribution of CASP values will be monitored and modelled by the study statistician. It is possible that fewer people will need to be screened to identify the required number of participants for the LOW CASP and HIGH CASP cohorts with the desired CASP separation.

Once identified, people in the HIGH CASP (n=130) and the LOW (n=65) groups will be invited to return to the research unit to undergo cardiac MRI for detailed evaluation of left ventricular mass index (LVMI) and cardiac and vascular structure and function. This evaluation will dictate whether the TREAT CASP study progresses to the stage 2 randomised clinical trial and observational follow-up study.

6.3.1.9 STOP/GO Checkpoint:

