6.7.1 Sample Size for the Stage 2 Randomized Clinical Trial

The Primary Outcome Measure for the Stage 2 randomised clinical trial is the change in left ventricular mass index from baseline to study end between the intervention group (BP lowering) and the no treatment (usual care) group. No published data is available relating to the effects of treatment upon LV mass in young men without established cardiovascular disease. Therefore the sample size for the RCT (study stage 2) is based on an analysis of previously published data investigating the effects of BP lowering treatment on MRI-determined LV mass index (LVMI) in people with existing cardiovascular disease. Analysis of data taken from 4 individual treatment studies comprising 7 active treatment arms in 627 individuals, mean age 60±3.4 years (51-54), indicates an average difference in LVMI between treatments (treatment versus no treatment) of 6.6g/m², SD 10.9g/m² [Appendix, table 2]. All treatments in the cited studies used inhibitors of the renin-angiotensin system and achieved moderate reductions in blood pressure (average reduction with treatment -8/-4.5 mmHg). Based on an anticipated difference in LVMI between treatments of 6.6g/m², SD 10.9g/m², power calculations indicate a sample size of 58 people per treatment arm will be required to show a difference with 90% power at p=0.05 in LVMI between the treatment and no treatment groups for the RCT (study stage 2). Recruitment of 65 individuals per treatment arm will allow for 10% drop-out between treatments.

6.7.1.1 Justification for the specified duration of the RCT in stage 2.

The duration of the stage 2 RCT in the TREAT CASP study is 12 months. Prior studies of LVMI change in response to BP-lowering therapy indicate that the majority of LVMI regression occurs within the first 12 months of treatment with very little additional change with longer follow-up (up to 5 years), ^(55,56). This is because LVMI regression is powerfully determined by the extent of the reduction in BP on treatment, and the BP change is maximal during the first year of therapy. Thus, the anticipated change in BP with treatment and the proposed study duration has been chosen to maximise the change in LVMI within a reasonable timescale for the RCT.

6.7.2 Sample size underpinning the STOP/GO check point at the end of the stage 1 Screening Study

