6.10.4 Statistical Methods

6.10.4.1 Statistical Analysis Plan:

Study data will be analysed at three time points:

- At the end of the stage 1 screening study, demographic, clinical chemistry and haemodynamic study data will be analysed in a cross-sectional analysis.
- After the initial cMRI, the STOP/GO checkpoint analysis will be performed and cMRI data will be analysed together with stage 1 study data in cross-sectional analyses.
- At the end of the stage 2 RCT and observational follow-up study primary, secondary and other endpoints will be analysed and a longitudinal data analysis will be performed.

6.10.4.2 Statistical Methods – Outcomes:

STAGE 1: Central aortic systolic pressure (CASP) distribution will be used to stratify participants as potential candidates for stage 2. Participants with CASP values above the 75th percentile will be candidates for randomisation into the trial. Simple, unrestricted randomisation will be used. Those with CASP less than the 25th percentile will be offered participation in the observational follow-up part of stage 2.

STAGE 2: All analyses for outcomes in the RCT will be carried out on the basis of the originally assigned groups, whether participants complete treatment or not as per CONSORT guidelines ⁽⁸⁷⁾. Multilevel mixed-effects linear regression models with a maximum likelihood estimator will be used and will account for the repeated measures nature of the data. These models are inherently robust to missing data, dealing with missing values in a similar manner to multiple imputation approaches.

The principal outcome for assessment will be change in LV mass index over the 1-year follow-up period. This will be compared between the two groups without adjustment and then with adjustment for potential confounders in multivariable models. Such additional variables will include, but not be limited to, age, brachial artery systolic pressure, smoking history and measures of adiposity such as BMI. Over-fitting of models will be avoided by careful attention to the adjusted r²

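### The upper 25% of 500 screened men is 125, not 130, and nothing allows for loss before randomisation, so the stated trial size and power are not secured; the LOW CASP group also has two definitions

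*Protocol*

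**What the plan says.** **HIGH group.** Section 6.3.1.8 describes selection once 500 men have been recruited: "we will select the upper 25% of CASP values to define the HIGH CASP group (n=130". Section 6.10.4.2 repeats the rule: "Participants with CASP values above the 75th percentile will be candidates for randomisation into the trial". Section 1.3 gives the planned flow as "500 participants recruited into the screening study with 130 then going on to be randomised into the clinical trial". Section 6.6 has the HIGH group, again 130, invited to the RCT.

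**Sample size.** Section 6.7.1 derives 58 per arm for 90% power and adds: "Recruitment of 65 individuals per treatment arm will allow for 10% drop-out between treatments".

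**Size of stage 1.** Section 6.3.1.8: "We plan to screen up to 500 participants in Stage 1 of the study", and then "It is possible that fewer people will need to be screened". Section 6.7 says instead that stage 1 recruitment can flex so that enough men are found, and gives no number. Section 6.3.1.7 gives an approximate 500.

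**LOW group.** Section 6.3.1.8: "We will also select 65 participants with the lowest CASP values who will form the LOW CASP observational cohort". Section 6.10.4.2: "Those with CASP less than the 25th percentile will be offered participation in the observational follow-up part of stage 2". Section 6.6 splits the men into upper and lower quartiles, calls these the HIGH and LOW groups, and invites both to cMRI.

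**The concern.** The protocol equates a percentile rule with a head count, and at 500 screened the two do not agree. The head count is also the number to be randomised, so every man in the HIGH group would have to accept cMRI and then accept randomisation, up to 18 months after his screening visit. The only allowance in the calculation, 10%, is for drop-out from the RCT.

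Loss before randomisation is foreseeable from the protocol itself. Under 6.3.1.6 and 6.3.1.7 eligibility at enrolment rests on history. ABPM, ECG, urine and blood tests come afterwards, and ABPM is there to remove white coat hypertension. Section 6.6 provides for men who leave after screening or after the first cMRI.

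If rule and number cannot both be met, someone must choose between fewer randomised men and a lower HIGH cut-off after the CASP values are known. The second choice changes the trial population.

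The LOW wording raises a separate question. It decides who is scanned, who enters the STOP/GO t-test (6.10.4.2.3), and which men form the reference for regression of LVMI (6.4.8).

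**Working it through.** **Inputs.** Difference 6.6 g/m², SD 10.9 g/m², 90% power, p=0.05, 10% drop-out (6.7.1); two-sided testing assumed, since sidedness is not stated. Expected loss below 5% (6.10.2.2). 500 screened and upper 25% (6.3.1.8). Uptake from the HIGH group to randomisation: not given, so a range is assumed.

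**1. The stated sample size reproduces.** n per arm = 2(1.960 + 1.282)² × (10.9/6.6)² = 57.3, rounded up to 58 (58.3 with the t distribution). 58/0.90 = 64.4, rounded up to 65 per arm, so 130 in total.

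**2. The stated HIGH group does not.** 0.25 × 500 = 125. Conversely, 130/500 = 26%, and 130/0.25 = 520 screened.

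**3. Effect of 125 instead of 130, all randomised (two-sample t power).**

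| Randomised | Later loss | Completers per arm | Power |
|---|---|---|---|
| 130 | 10% | 58.5 | 90.1% |
| 125 | 10% | 56.25 | 88.9% |
| 125 | 5% | 59.4 | 90.5% |

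**4. Margin.** The target is 2 × 58 = 116 completers. At 10% loss, 116/0.90 = 128.9, so 129 must be randomised, more than the 125 candidates. At 5% loss, 116/0.95 = 122.1, so 123 of the 125 (98%) must be randomised.

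**5. Effect of incomplete uptake.** Completers per arm = 125 × uptake × 0.90 / 2. Stage 1 number for 130 randomised = 130/(0.25 × uptake). If 500 are screened and 130 are still to be randomised, the share that must be invited = 130/(500 × uptake).

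| Uptake (assumed) | Randomised from 125 | Completers per arm | Power | Stage 1 number for 130 | Share of 500 invited for 130 |
|---|---|---|---|---|---|
| 100% | 125 | 56.2 | 88.9% | 520 | 26% |
| 90% | 112.5 | 50.6 | 85.5% | 578 | 29% |
| 80% | 100 | 45.0 | 81.1% | 650 | 33% (32.5) |
| 70% | 87.5 | 39.4 | 75.6% | 743 | 37% |

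**6. LOW group.** The 65 lowest are 65/500 = 13%; the lower quartile is 125 men. The number scanned is 130 + 65 = 195 under 6.3.1.8, or 125 + 125 = 250 under 6.6. On the figures in 6.7.2 (10 g/m², SD 11.8), the STOP/GO comparison of 65 LOW with 125 HIGH has power above 99%. With the SD raised by 50% to 17.7, power is about 96%. A LOW group of 125 would give more at the same difference.

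**The case against.** The strongest reply is that the slip is small and the plan has room to absorb it. Most of that stands.

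- **Power.** A reader might infer that the trial cannot deliver its 90%. The documents do not support that. With all 125 randomised the loss is about one point, and at 5% loss, just above the level the protocol expects, power is still 90.5%. Anything larger depends on an uptake figure that the protocol does not give.
- **Uptake.** Unwillingness to have MRI is an exclusion criterion (6.3.1.3), and 6.3.1.6 asks for consent to randomisation at entry. Both should limit refusal. However, 6.6 still invites the men to the RCT, and its schedule shows a second signed consent at randomisation.
- **Flexible recruitment.** Section 6.7 links flexibility to powering the RCT, and 6.3.1.8 has the statistician monitor the CASP distribution to find the required numbers. One can fairly read 500 as a planning figure. Yet 6.3.1.8 sets it as an upper limit and foresees fewer, and 6.7 names no ceiling. The two sections conflict, and the conflict does not show that 130 is out of reach.
- **Post-enrolment exclusions.** The protocol does not say whether men excluded by testing still count in the 500, and it gives no exclusion rate. That they reduce the pool is an inference.
- **LOW group.** A reader might call the two definitions mutually exclusive. They are nested: the 65 lowest lie within the lower quartile, and 6.10.4.2 can be read as describing a candidate pool. Sizing on quartiles is also conservative for a contrast that uses the lowest 13%. What remains is that 6.6 sends the whole lower quartile to cMRI and does not say which 65 of them are then followed.

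**Conclusion.** The point holds in a limited form. At 500 screened, the upper-quartile rule gives 125 candidates, so 130 cannot be randomised even with full uptake; that would need 520 men or a top-26% rule. The direct cost is about one power point: 88.9% against 90.1% at 10% loss.

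The more important weakness is the lack of any margin before randomisation. Under assumed uptake of 90%, 80% or 70%, and 10% later loss, power would be about 85%, 81% or 76%. These figures illustrate the sensitivity and are not forecasts. They rest on the protocol's own 6.6 and 10.9 g/m² and on a two-sided test. The right conclusion is that the stated size and power are not secured, which is weaker than saying they fail.

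The LOW group needs one definition because the wording changes who is scanned (195 or 250 men), who enters the STOP/GO test and who serves as the reference cohort. It has no bearing on RCT power, and STOP/GO power stays at about 96% or more even with the SD raised by half.

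**What to change.** 1. **HIGH group and RCT size.** Choose one. Either keep the 75th percentile and restate the expected number randomised and the power at a stated uptake; or define HIGH by rank, inviting in descending order of CASP until 130 are randomised, with the lowest percentile allowed fixed in advance. Make 1.3, 6.3.1.8, 6.6, 6.7.1 and 6.10.4.2 agree.
2. **Stage 1 size.** Reconcile the limit of 500 in 6.3.1.8 with the flexibility in 6.7 by giving one ceiling that matches the stated uptake (for example 578 at 90% or 650 at 80%, if the quartile rule and 130 are both kept). Say whether men excluded by post-enrolment tests count towards it.
3. **LOW group.** Use one definition, either the 65 lowest or the lower quartile, for cMRI, the STOP/GO test and follow-up, in 6.3.1.8, 6.6 and 6.10.4.2. If the quartile is kept, say how the 65 to be followed are chosen.

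The cost is protocol wording, with one consequence that depends on the choice: a slightly less favourable stated power, an explicit and somewhat lower HIGH threshold, or, if the ceiling is raised, more men to screen.

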1. There are approximately 1 million younger people with a possible diagnosis of stage 1 hypertension in the UK ⁽³⁾. The simple non-invasive measurement of CASP will potentially lead to better stratification of those requiring treatment for their hypertension. This could avoid the spurious diagnosis of hypertension due to excess pressure amplification from their aortic root to brachial artery.

- 2. The use of CASP to stratify people for treatment could avoid the unnecessary treatment of some people with stage 1 hypertension in whom the CASP value is normal and in whom, as we propose, there may be no evidence of cardiovascular structural damage either at baseline, or after 12 months of follow-up.
- 3. The use of CASP to stratify people for treatment could identify those who have evidence of early cardiovascular structural damage at baseline and who would benefit most from treatment to lower blood pressure.
- 4. Targeting of treatment to those with the highest CASP values who show evidence of early cardiovascular structural damage could result in regression of structural damage, and over the longer term, would result in a reduced lifetime risk of cardiovascular morbidity and mortality.
- 5. This could lead to economic benefit and better use of health care resources i.e. improving diagnosis and targeting effective treatment to those at highest risk.
- 6. This study addresses a key research question identified by the current NICE hypertension guidelines ⁽⁴⁾ regarding the need for more research data on how to best stratify younger people with stage 1 hypertension for treatment.
- MRI scanning is non-invasive and does not involve exposure to ionizing radiation. There are no known long-term side-effects from MRI. Allergic reactions to MRI contrast occur rarely (~1/10,100) and patients with significant renal failure will be excluded which essentially eliminates any risk of nephrogenic systemic fibrosis.

5.1.8.2 Potential Risks of using CASP to stratify younger people for treatment of stage 1 hypertension:

- The use of CASP may fail to differentiate between those with and without early cardiovascular structural damage when comparing people with LOW and HIGH CASP values. This finding would eliminate the need for a clinical trial of blood pressure lowering in those with HIGH CASP values and the study would be terminated without performing a clinical trial in patients with stage 1 hypertension.

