A STOP/GO checkpoint has been incorporated into the study design which will be evaluated before the study proceeds to the second stage. The STOP/GO checkpoint will be implemented to avoid futility in implementing the second part of the study i.e. if there is no difference in cardiac structure between the HIGH and LOW CASP cohorts there would be little likely benefit in stratifying participants by their central BP for subsequent treatment for blood pressure lowering.

Cardiac MRI (cMRI) will be used to measure left ventricular mass index in participants from the HIGH and LOW CASP groups participating in the stage 1 screening study. This data will be used to evaluate

the STOP/GO checkpoint. If a difference in LVMI is observed between participants from the HIGH and LOW CASP groups, the null hypothesis that there is no difference in LVMI between groups will be rejected and the study can proceed to the second stage. If the null hypothesis is not rejected i.e. if there is no difference in LVMI between people from the HIGH and LOW CASP groups, the TREAT CASP study will be terminated at this point. This evaluation will be used to confirm or refute the first key element of our hypothesis, i.e. whether CASP has been effective at identifying patients with and without pressure-related target organ damage, irrespective of their brachial blood pressure values.

The decision to proceed to the second stage of the study will be taken by the Trial Steering Committee. The data upon which the STOP/GO decision is made will be reviewed by an independent statistician who will provide recommendations to the Trial Steering Committee.

6.3.1.10 STAGE 2 Randomised Clinical Trial and Observational Follow-up Study:

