The inbuilt STOP/GO checkpoint to allow the study to proceed to the RCT (stage 2) is based on achieving a significant difference in LVMI as measured by MRI between people in the HIGH CASP and LOW CASP groups at the end of the screening phase (stage 1 see section 6.3.1.7).

Previously published studies indicate that LVMI is directly related to blood pressure and that the relationship between the change in systolic blood pressure and the change in LVMI approximates to the order of $1g/m^2$ LVMI per mmHg SBP ^(57,58). This order of magnitude of change is similar to that seen for the regression in LVMI with BP-lowering treatment in the analysis of published studies for the RCT power calculation (average reduction in SBP -8 mmHg, average reduction in LVMI with treatment -6.6 g/ m^2). Preliminary data from our clinical laboratory in men with stage 1 hypertension stratified by their CASP values indicates that groups incorporating the highest and lowest 25% of the population with regard to their CASP values are separated by brachial systolic blood pressures of at least 10mmHg [Appendix, figure 7]. Based on the relationship between LVMI and BP as outlined above, this indicates a likely separation between groups in LVMI of approximately $10g/m^2$. With regard to a starting value, systematic review of LVMI values by MRI in 1,032 young men from 11 published studies indicates a mean value of 78.5 g/m², SD 11.8g/m² ($^{59-67}$). Combining an estimated 10g/m² difference between the HIGH and LOW CASP groups with the SD for LVMI in young men, indicates a sample size of 31 per group would be required to demonstrate a difference in LVMI with 90% power at p=0.05. This indicates that a sample size of 65 individuals in the LOW CASP and 130 individuals for the HIGH CASP group should have abundant power to demonstrate a difference in LVMI at the study STOP/GO checkpoint. This will provide a robust basis to confirm or refute our hypothesis that CASP provides an effective mechanism for identifying patients with and without pressure-related target organ damage, in people with a diagnosis of stage 1 hypertension.

6.7.2.1 Consideration of variability in LVMI:

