LVMI may be more variable in young people when compared to more frequently studied older populations. This could potentially impact upon the degree of separation in LV mass between the high and low CASP groups at the end of the first study phase (stage 1 screening study). However, this potential variability has already been taken into consideration in that the studies used to power the first phase of the study focus predominantly on younger people. Moreover, the power calculation used to power the STOP/GO checkpoint is sufficiently conservative to allow an increase in the standard deviation for LV mass index of up to 50%, equivalent to the highest levels for the standard deviation in LV mass in the group of studies upon which our study is powered, before power becomes marginal. Variability in LV mass could also potentially relate to the inclusion of fit
young men with physiological LVH. However, detection of overt LVH by ECG at screening is an exclusion criterion for the study.

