of the models. Thus, only coefficients that significantly improve the fit of the models or where a strong case for their known biological importance can be made will be included. Results will be presented in a multi-stage format so that readers can assess the unadjusted and adjusted models separately. Where predictor variables are suspected to have a non-linear influence on outcome (e.g. on LV mass index), further polynomial terms may be added (e.g. quadratic and cubic) but careful examination of model fits to raw data will be made to prevent such models from over-fitting the data in a spurious sense. Where interactions between predictor variables are suspected on the basis of biological plausibility e.g. varying influence of adiposity on LV mass index with age, the appropriate interaction terms will be added to the models to assess this. Outliers will be dealt with on a case-by-case basis and excluded if values are biologically implausible or can be found to be erroneous after reference to the raw data.

No interim analyses will be performed in accordance with the blinded nature of the study. Results will be reported as per CONSORT guidelines ⁽⁸⁷⁾.

6.10.4.2.1 Data Manipulation:

In all cases, parametric analyses will be preferred and applied to data with normal distributions or after appropriate transformation to normality e.g. Log transformation for right-skewed data.

6.10.4.2.2 Missing Data:

For missing data appropriate procedures will be used such as multiple imputation procedures or (where y-values are (MAR) missing at random), the bootstrap approach as suggested by Efron ⁽⁸⁶⁾.

6.10.4.2.3 Analysis of the STOP/GO Checkpoint:

It is a STOP/GO condition of the study prior to stage 2 that the high and low CASP groups must have a significant (P<0.05) difference in LV mass index. Student t-test comparison of the groups will be used to assess this.

6.10.4.2.4 Economic evaluations:

No economic evaluations are planned. Evaluation of cost effectiveness of the study medications in terms of quality adjusted life years (QALYs) is well established ⁽⁴⁾.

6.10.4.2.5 Additional Analyses – Subgroup:

No additional analysis in sub-groups is planned.

6.10.4.2.6 Additional Analyses - Adjusted:

No additional analysis in sub-groups is planned.

6.10.4.2.7 Analysis Population and Missing Data:

The analysis population and strategies for dealing with missing data are outlined in section 6.10.4.2 – statistical methods.

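### A non-significant STOP/GO test is read as no LVMI difference and as able to refute the CASP hypothesis, although it can leave real gaps smaller than the planned 10 g/m² open

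*Protocol*

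**What the plan says.** Section 6.3.1.9 (STOP/GO Checkpoint) glosses non-rejection of the null hypothesis as there being no "difference in LVMI between people from the HIGH and LOW CASP groups, the TREAT CASP study will be terminated at this point". The same paragraph says that the evaluation will either confirm or refute the first element of the hypothesis, namely that CASP separates men with pressure-related organ damage from men without it.

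Three other places bear on this:

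- Section 6.10.4.2.3 sets the rule: "the high and low CASP groups must have a significant (P<0.05) difference in LV mass index". It adds that "Student t-test comparison of the groups will be used to assess this".
- Section 6.7.2 says of the 65 and 130 men: "This will provide a robust basis to confirm or refute our hypothesis".
- Section 5.1.8.2 says of a failure of CASP to separate the groups: "This finding would eliminate the need for a clinical trial of blood pressure lowering in those with HIGH CASP values".

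None of these sections names an LVMI gap that the data must exclude before the hypothesis counts as refuted. None provides for an inconclusive result. Section 6.3.1.9 leaves the decision with the Trial Steering Committee, advised by an independent statistician.

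**The concern.** A test that fails to reach P<0.05 says that the data are compatible with no difference. It does not say which real differences they rule out; the confidence interval does that. The protocol moves from non-rejection to absence of a difference, and from there to refutation. Followed as written, an inconclusive comparison would count against the study's first hypothesis.

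The decision not to start stage 2 is a separate matter. Section 6.3.1.9 gives its purpose as avoiding futility, and a significance rule can serve that purpose. At stake is the scientific conclusion attached to a STOP. This is text that the protocol itself fixes, so it is not a detail left to a statistical analysis plan.

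**Working it through.** **Inputs**

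- Planned gap 10 g/m², SD 11.8 g/m², 90% power, p=0.05: section 6.7.2.
- Group sizes at the checkpoint, 130 HIGH and 65 LOW: section 6.7.2.
- Stress SD: section 6.7.2.1 calls the calculation conservative enough "to allow an increase in the standard deviation for LV mass index of up to 50"%, so 1.5 × 11.8 = 17.7 g/m².
- RCT target effect 6.6 g/m²: section 6.7.1.
- Assumption: a two-sided test. The protocol does not state the sidedness, but a two-sided test reproduces its sample size.

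**The plan's own figure.** Section 6.7.2 "indicates a sample size of 31 per group would be required to demonstrate a difference in LVMI with 90% power at p=0.05". The normal approximation, 2 × (1.960 + 1.282)² × 11.8² / 10², gives 29.3, rounded up to 30 per group. The two-sample t-test version gives 30.25, rounded up to 31. The stated figure is reproduced.

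**What a non-significant result can exclude at 130 v 65**

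SE = SD × √(1/130 + 1/65) = SD × 0.1519. The critical difference is t(0.975, 193 df) × SE, with t = 1.972. A result just short of significance has a 95% interval running from about 0 to twice the critical difference, so that is the largest upper limit a non-significant test can have.

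| SD (g/m²) | SE | Critical difference | Largest upper limit |
|---|---|---|---|
| 11.8 | 1.79 | 3.54 | 7.07 |
| 17.7 | 2.69 | 5.30 | 10.61 |

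The largest upper limit is 2 × 1.972 × 0.1519 × SD, or about 0.599 × SD. It stays below 10 while the SD is below 10 / 0.599 ≈ 16.7. It exceeds 6.6 once the SD is above 6.6 / 0.599 ≈ 11.0.

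**Chance of a non-significant test when a real gap exists** (1 minus noncentral-t power, 193 df, noncentrality = gap / SE)

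| True gap (g/m²) | SD 11.8 | SD 17.7 |
|---|---|---|
| 10 | under 0.1% | 4.1% |
| 6.6 | 4.4% | 31.5% |
| 5 | 20.7% | 54.4% |
| 4 | 39.7% | 68.4% |

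**How often 6.6 g/m² is left open.** The interval from a non-significant result includes 6.6 when the observed gap lies between 6.6 minus the critical difference and the critical difference.

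- SD 11.8: between 6.6 − 3.54 = 3.06 and 3.54. The chance (normal approximation) is at most about 10% over the true gaps tried, from 0 to 6.6.
- SD 17.7: between 6.6 − 5.30 = 1.30 and 5.30. The chance is 29% to 54% over the same true gaps.

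**How often the planned 10 g/m² is left open.** At SD 11.8, never. At SD 17.7, only for observed gaps between 10 − 5.30 = 4.70 and 5.30.

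**The case against.** The strongest reply is that the protocol predicts a gap of 10 g/m² and has ample power for it. At SD 11.8 power exceeds 99.9%, and every non-significant result has an upper limit of at most 7.07. Non-rejection would then refute the gap that was predicted. This stands at the planning SD. However, the protocol does not limit its conclusion to that gap. It speaks of no difference at all, and of whether CASP identifies organ damage.

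A second reply is that 17.7 is a tolerance limit and not the expected SD. That is right, and the figures at 17.7 should be read as a stress case. The protocol itself supplies that limit, though, because it accepts that LVMI may vary more in young people.

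A third is that the Trial Steering Committee takes the decision with independent statistical advice. That gives room for judgement in practice, but the termination wording and the mandatory P<0.05 condition leave no stated category for an inconclusive result.

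Two stronger readings are tempting, and the documents do not support them:

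- A reader might infer that a STOP routinely leaves open a gap larger than the RCT's own target. The 6.6 g/m² is a treatment difference in LVMI change, not a cross-sectional gap between CASP groups. At SD 11.8 it is exceeded only narrowly, and at an SD of 10.9 the largest upper limit is 6.53, below it. It is a rough benchmark only.
- A reader might infer that an inconclusive result would be published as a negative one. Section 7.11.1 commits to publishing whatever the direction of effect, but no section prescribes how a STOP would be worded.

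**Conclusion.** The point holds as a fault in the stated conclusion, not in the stopping rule. Non-significance at STOP/GO does not establish that HIGH and LOW CASP men have equal LVMI, and by itself it does not refute the hypothesis.

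The size depends on the SD and on the gap considered. At the planning SD the planned 10 g/m² is excluded, but true gaps of 4 to 5 g/m² would be missed about 40% to 21% of the time. At the stress SD those figures are about 68% and 54%, and even 10 g/m² may not be excluded.

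These results assume a two-sided t-test, all 130 and 65 men with usable scans, and a common SD. With an assumed 10% loss of scans (117 v 58), the largest upper limits rise to 7.48 and 11.22 g/m². The correction is worth making because it changes what the study may conclude from a STOP at almost no cost.

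**What to change.** - Keep P<0.05 as the operational futility rule for not starting stage 2, if the Trial Steering Committee wants it.
- Reword sections 5.1.8.2, 6.3.1.9 and 6.7.2 so that non-rejection means that a difference was not shown.
- Base the checkpoint conclusion on the HIGH-LOW difference in LVMI with its 95% confidence interval.
- Reserve the statement that the hypothesis is refuted for an upper limit below a cross-sectional LVMI gap that the sponsor names and justifies before the checkpoint. The planned 10 g/m² is the only gap that the protocol states for this comparison. If it is chosen, the claim should be limited to refuting a gap of that size.

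The cost is wording in three sections, one interval and one pre-stated value, with no extra participants or scans. The drawback is that a STOP becomes less decisive: some results that now count as refutation would be reported as inconclusive.
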